### 12.1.11 Safety Reporting

The PI will make reasonable and consistent efforts to document all adverse events (AEs). The PI will:

- record every AE and observed device deficiency or malfunction
- report all SAEs and device deficiencies to the sponsor within 48 hours of occurrence
- provide sponsor-requested details for AEs and device deficiencies/malfunctions in a timely manner
- report SAEs to the EC per EC guidelines
- submit a summary of the progress of the study to the involved ethics committee once a year or according to the national/local requirements

### 12.1.12 Device Accountability

Device accountability records must be maintained at the study site. All investigational devices will be traced by part number, lot number, and if applicable, serial number. The investigator is responsible for accounting for all devices transferred to his position. The investigator will ensure that any devices stored at the site are in a secure location.

The sponsor will ensure that investigational devices are tracked carefully from the time of provision to the site to disposition.

### 12.1.13 Recording Data on Electronic CRFs

The data will be entered via electronic interface through an Electronic Data Capture system (database), validated and secured with compliant requirements such as audit trail, secure log-in with the PI responsible for reviewing the electronic data and signing using the database system signature method.

The study will use electronic case report forms that have been standardized for the study to collect data. Site personnel will be trained in use of the eCRFs before study initiation. The PI will ensure that data recorded in the eCRFs in a timely manner and are accurate, consistent with source documents, reliable and logically correct.

 Cerus Endovascular	Document Number DNQS428-01	Rev. F	Page 52 of 119
Clinical Investigation Plan	Title		
Confidential & Proprietary	Coil Assisted Flow Diversion: A prospective, single arm, multi-center study to assess the safety and performance of Neqstent in adjunctive therapy (CAFI Study)		

The database will include built in edit checks which will facilitate data cleaning by identifying missing, illogical or inconsistent data at the time of entry. Monitors or other data reviewers may also enter manual queries to request additional data clarifications. Queries will be managed within the EDC as per Data Management Plan (document DNQS428-06) herewith enclosed in APPENDIX-E.

The Data-Management Plan will be developed to describe:

- a) Procedures used for data review, database cleaning, and issuing and resolving data queries
- b) Procedures for verification, validation and securing of electronic clinical data systems
- c) Procedures for data retention
- d) Specified retention period
- e) Other aspects of clinical quality assurance, as appropriate

Electronic CRF Form samples are in APPENDIX F – Case Report Form CRF .

#### **12.1.14 Deviations**

The investigator is not allowed to deviate from the Clinical Investigational Plan, except to maintain the subject's rights, protect the life and physical well-being of a subject in an emergency, or the scientific integrity of the investigation. All protocol deviations shall be documented on the Protocol Deviation Case Report Form.

The sponsor (or delegate) is responsible for analyzing deviations, assessing their significance, and identifying any additional corrective and/or preventive actions (e.g. amend the Clinical Investigational Plan, conduct additional training, or terminate the investigation). Repetitive or serious investigator compliance issues may result in initiation of a corrective action plan with the investigator and site, and in some cases, necessitate suspending enrollment until the problem is resolved or ultimately terminating the investigator's participation in the study.

#### **12.1.15 Final Report**

The sponsor will prepare a final report when the study has fulfilled the data requirements. The sponsor will provide the report to the EC and regulatory authorities as required, as well as to the notified body.

#### **12.1.16 Document Retention**

The PI will maintain documents related to this investigation until 2 years after the study is complete or in accordance to EU or individual site requirements. The PI may transfer custody of records to another person/party and document the transfer at the clinical site with notification to the sponsor or at the sponsor's facility. The PI and/or site personnel cannot destroy the study documents without first obtaining written approval from the sponsor. Required documents to retain are extensive and are listed in Annex E of ISO 14155:2011(E).

#### **12.1.17 Source Documents**

The PI will retain original source documents (or copies thereof) used to verify study data. The PI or site personnel will provide written confirmation with signature and date that copies of source

 Cerus Endovascular	Document Number DNQS428-01	Rev. F	Page 53 of 119
Clinical Investigation Plan	Title		
Confidential & Proprietary	Coil Assisted Flow Diversion: A prospective, single arm, multi-center study to assess the safety and performance of Neqstent in adjunctive therapy (CAFI Study)		

documents are true reproductions of the original source document. The sponsor may have access to original source documents upon request.

## 12.2 Sponsor Responsibilities

### 12.2.1 Overall Conduct of Study

Cerus Endovascular, Ltd, the study sponsor, is responsible for the overall conduct of this investigation, including:

- implementing written clinical quality procedures to ensure that the clinical investigation is designed, conducted and monitored, and that data are generated, documented, recorded and reported in compliance with Good Clinical Practice (GCP), the CIP and its amendments, and any other applicable standards and regulatory requirements
- maintaining records to document the compliance of all parties involved in the clinical investigation
- documenting significant/key correspondence with all parties involved in the clinical investigation
- ensuring that the clinical investigation is appropriately monitored by determining the extent and nature of monitoring
- reviewing monitoring reports and following up any required actions in those reports
- taking prompt action to secure compliance with all clinical investigation requirements
- submitting progress reports, including safety summary and deviations, when requested, to all reviewing ECs and the regulatory authorities
- providing insurance, in accordance with national regulations, covering the costs of treatment of subjects in the event of the study related injuries.

### 12.2.2 Clinical Personnel

The sponsor will designate or appoint one or more study monitors and will ensure documentation of training of monitors sufficient to conduct the investigation.

### 12.2.3 Study Preparation

Before starting the study, the sponsor will:

- define all roles and responsibilities related to this investigation
- ensure that all required signatures are obtained
- ensure the accuracy of translation, if required, of any aspect of the study prior to initiating the study at the selected site
- develop a complete set of documents necessary to begin the study, including consent forms, case report forms (CRFs) and, if required, an investigator's brochure
- document any financial arrangements between the PI or investigation site and the sponsor

 Cerus Endovascular	Document Number DNQS428-01	Rev. F	Page 54 of 119
Clinical Investigation Plan	Title		
Confidential & Proprietary	Coil Assisted Flow Diversion: A prospective, single arm, multi-center study to assess the safety and performance of Neqstent in adjunctive therapy (CAFI Study)		

- submit any required application(s) to begin the investigation to appropriate regulatory authorities for review, acceptance or permission, as required
- ensure documented EC approval before the study is started
- ensure documented ongoing EC approval of the study
- ensure that the site's ICF is consistent with requirements of ISO 14155:2011
- ensure that any modifications required by the EC or regulatory authority are made and documented by the PI

#### 12.2.4 Study Documentation Amendment

The IB, CIP, CRFs, informed consent form and other subject information, or other clinical investigation documents shall be amended as needed throughout the clinical investigation, and a justification statement shall be included with each amended section of a document. Proposed amendments to the CIP shall be agreed upon between the sponsor and principal investigator, or the coordinating investigator. The amendments to the CIP and the subject's informed consent form shall be notified to, or approved by, the EC and regulatory authorities. The version number and date of amendments shall be documented. For non-substantial changes [e.g. minor logistical or administrative changes, telephone numbers, renewal of insurance] not affecting the rights, safety and well-being of human subjects or not related to the clinical investigation objectives or endpoints, a simple notification to the EC and, where appropriate, regulatory authorities can be sufficient.

#### 12.2.5 Investigational Site Qualification

The sponsor will ensure that each investigational site:

- has a qualified PI
- has adequate staff, resources, including facilities, laboratories, equipment and a qualified investigation site team
- has access to an adequate number of subjects on a timely basis

Site qualification will be documented.

#### 12.2.6 Investigational Site Initiation

The sponsor will ensure that the site does not begin the study until all of the following have been collected or performed and documented:

- training in requirements and contents of this CIP and its associated documents (e.g., CRFs, IFU, IB, etc.)
- written EC approval, including EC-approved IC form, if required
- list of EC members or EC assurance number, if required
- documentation of investigational team's designated roles and responsibilities
- documentation of investigator conflict of interest

 Cerus Endovascular	Document Number DNQS428-01	Rev. F	Page 55 of 119
Clinical Investigation Plan	Title		
Confidential & Proprietary	Coil Assisted Flow Diversion: A prospective, single arm, multi-center study to assess the safety and performance of Neqstent in adjunctive therapy (CAFI Study)		

- signed investigator agreement
- signed clinical trial agreement (CTA). The CTA is the legal agreement between the site, PI and sponsor that covers all activities related to the study. The agreement will indicate that, by participating in a clinical investigation, the parties may share some regulatory responsibilities with the sponsor.
- current curriculum vitae of PI and any sub-investigators

### 12.2.7 Monitoring

Monitoring will be performed during the study according to the Study Monitoring Plan.

The sponsor and/or sponsor delegate is responsible for study monitoring. Monitoring is done to verify that the study has been performed consistent with this CIP (and its amendments), and any other local or national requirements. The sponsor will document a study monitoring plan.

### 12.2.8 Qualified Monitors

The sponsor will ensure that study monitors:

- understand requirements of this CIP
- are knowledgeable on the use of the study device
- are knowledgeable on the informed consent process
- are trained on the applicable portion of the sponsor's quality control system
- are trained in any special procedures required for monitoring this CIP

Training will be documented in the sponsor's files.

### 12.2.9 Remote Monitoring

Data collected during the study will be systematically reviewed by the sponsor to identify inconsistencies, potential data errors or potentially unclear information. Statistical techniques may be used to identify outliers. Queries will be sent to the site for data that may represent errors or that require clarification.

### 12.2.10 On-Site Monitoring

The monitor will perform on-site monitoring visits to verify:

- compliance with this CIP and its amendments
- compliance with requirements, if any, of the governing /EC
- compliance with local regulations pertaining to a clinical study
- compliance with requirements, if any, of regulatory authorities
- continued adequacy of investigation site resources, including laboratories, equipment and the investigation site team
- continued access to a sufficient number of potential study subjects

 
Cerus Endovascular
	
Document Number DNQS428-01
	
Rev. F
	
Page 56 of 119

Clinical Investigation Plan
	
Title
		

Confidential & Proprietary
	
Coil Assisted Flow Diversion: A prospective, single arm, multi-center study to assess the safety and performance of Neqstent in adjunctive therapy (CAFI Study)
		

- compliance with the informed consent process
- all CIP requirements are met before the study begins at the site
- adequate storage, maintenance and accountability of investigational devices
- adequate storage and maintenance of source documents and other related records
- source documents are accurate, complete and up-to-date
- CRFs and queries are completed adequately, in a timely manner, and consistent with source documents
- all AEs, deviations and device deficiencies are documented and reported to the sponsor
- any device deficiencies/malfunctions that could have led to an SAE are reported to the sponsor without unjustified delay
- all SAEs are reported to the EC, if required
- maintenance of required reports, notifications, applications, submissions and correspondence in the PI's files
- maintenance and calibration (and documentation thereof) of all equipment relevant to this CIP
- maintenance and documentation of current laboratory normal values and certifications, if required
- subject withdrawal and reasons for withdrawal have been documented
- subject non-compliance with the requirements stated in the informed consent has been documented
- any corrective and preventive actions, as needed, have been implemented and are effective

The monitor will document site monitoring visits in a report that includes the site's compliance with the CIP. The report will include:

- date of monitoring
- site identification
- name of monitor and PI
- summary of what was reviewed
- summary of observations and findings
- summary of recommendations

The monitor will share all findings with the PI and the sponsor.

 
Cerus Endovascular
	
Document Number DNQS428-01
	
Rev. F
	
Page 57 of 119

Clinical Investigation Plan
	
Title
		

Confidential & Proprietary
	
Coil Assisted Flow Diversion: A prospective, single arm, multi-center study to assess the safety and performance of Neqstent in adjunctive therapy (CAFI Study)
		

### 12.2.11 Study Close Out

When the investigation is complete, the sponsor will ensure that sites undergo closeout activities, to include:

- all essential documents are available and present in the PI's files
- all CRFs are completed
- all queries are resolved
- the status of all ongoing AEs is documented
- arrangements for record retention have been made
- all documents needed for sponsor's files are retrieved
- unused study devices are accounted for and returned to the sponsor
- local EC and regulatory authorities are notified, if applicable

In addition, the sponsor will:

- provide a clinical investigation report to sites
- ensure that clinical investigational report is provided to EC, investigators and regulatory authorities (if required)

### 12.2.12 Auditing

At the discretion of the sponsor, any site may undergo audit by the sponsor or a sponsor-designated third party. Audits evaluate compliance with this CIP, ISO standards or other regulatory requirements.

### 12.2.13 Safety Reporting

The sponsor is responsible for ongoing safety evaluation in this CIP. Sponsor activities regarding safety include:

- ensuring the CEC reviews all serious neurologic, device and procedure related adverse events to ensure they are reported accurately and in sufficient detail
- review and classification of all AEs reported in the study
- confirm site's classification of AEs in terms of severity and relatedness to the study device
- review of device deficiencies and malfunctions, including determination and documentation of whether deficiencies/malfunctions could have led to an SAE
- ensuring the reporting of all SAEs and device deficiencies/malfunctions that could have led to an SAE to the EC and, if required, regulatory authorities in a timely fashion and informing all site PIs in writing of all SAEs at all sites in a timely fashion
- ensuring that the EC and the regulatory authorities are informed of significant new information about the clinical investigation

 Cerus Endovascular	Document Number DNQS428-01	Rev. F	Page 58 of 119
Clinical Investigation Plan	Title		
Confidential & Proprietary	Coil Assisted Flow Diversion: A prospective, single arm, multi-center study to assess the safety and performance of Neqstent in adjunctive therapy (CAFI Study)		

- updating the risk analysis and assessment of corrective or preventive actions potentially required as a result of new information obtained in the investigation

The sponsor will evaluate all serious adverse events. The sponsor will investigate each SAE to determine whether the event represents an unanticipated serious adverse device effect (USADE). The sponsor will report any event to regulatory authorities, investigators and reviewing ECs as necessary. If an investigation shows that a USADE presents an unreasonable risk to subjects, the sponsor will terminate all investigations or parts of investigations presenting that risk as soon as possible. The sponsor will only resume a terminated investigation after corrective actions have taken place, site investigators are informed and ECs have been notified and given approval to resume the study.

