### 6.1.1 Risk Mitigation

The manners in which risks shall be minimized for the device procedure include the following:

1. The PI and clinical site staff were chosen because of their expertise in the field of neurovascular procedures.
2. The physician(s) performing device-related procedures have received the appropriate training in the use of the device.
3. Subjects are being monitored/observed throughout the study by multiple-disciplinary site staff, trained in the management of patients with IAs.

 Cerus Endovascular	Document Number DNQS428-01	Rev. F	Page 28 of 119
Clinical Investigation Plan	Title		
Confidential & Proprietary	Coil Assisted Flow Diversion: A prospective, single arm, multi-center study to assess the safety and performance of Neqstent in adjunctive therapy (CAFI Study)		

4. Extensive pre-clinical, bench and *in vivo* testing was performed in order to optimize the device safety and function.
5. Sponsor Clinical Personnel shall provide oversight throughout the Study.

Experienced Clinical Monitors will perform on-site and remote Monitoring throughout the trial to ensure protocol compliance and compliance with ISO 14155:2011 and all applicable EC and competent authority (CA) regulations. Neqstent is being designed and developed in accordance with a risk management process that conforms with EN ISO 14971:2012. This process serves to identify hazards associated with the subject devices and accessories, estimate and evaluate the risks associated with those hazards, control (reduce) those risks, and monitor the effectiveness of that control. Risk management ensures that risks to the patient, users and third parties are minimized and determined to be acceptable. The risk management results are crosschecked against applicable risk reduction documentation to ensure the risk reduction measures are implemented.

The Cerus Endovascular design review process ensures that all identified risk reduction measures have been implemented. Residual risks, the risks remaining after risk control (i.e. risk reduction) measures have been taken, are addressed in the “Contraindications” and “Adverse Events” sections of the Instructions For Use as well as listed in Table 5.

Potential adverse events associated with use of Neqstent, some of which could be fatal or cause severe neurologic deficits, include:

- Aneurysm rupture causing intracranial hemorrhage
- Injury to parent artery causing thrombosis or hemorrhage

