# 9 Study Oversight

## 9.1 Clinical Events Committee (CEC)

A combined CEC/DSMB Committee will be established by Cerus Endovascular or designee to assess, review and classify all neurologic, device-related and procedure-related SAEs to ensure they are reported accurately. The CEC member(s) appointed for the study will be qualified by background, training and expertise in neurovascular treatment of IAs. The member(s) will not be an investigator on the study. The CEC will regularly review and adjudicate the adverse events and any deaths. Classification of the events will include device and procedure relatedness and seriousness. Member(s) will be provided data summaries and source documentation for review.

 Cerus Endovascular	Document Number DNQS428-01	Rev. F	Page 43 of 119
Clinical Investigation Plan	Title		
Confidential & Proprietary	Coil Assisted Flow Diversion: A prospective, single arm, multi-center study to assess the safety and performance of Neqstent in adjunctive therapy (CAFI Study)		

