## 9.2 Data Safety and Monitoring Board (DSMB)

A DSMB will convene of member(s) experienced in an associated discipline. The DSMB will review the study data after enrollment of the first five patients. Enrollment of further patients will occur as the DSMB reviews the data. The DSMB will provide a report following the review and advise Cerus Endovascular for any modifications or concerns that may be necessary. The DSMB will provide further evaluation at least twice per year and after the first 5 patients are enrolled. If slow enrollment occurs, the DSMB may meet less frequently. The CEC and DSMB will meet as a combined committee.

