## 11.5 Total Expected Trial Duration

It is expected that the study will take 6 months to enroll a minimum of 51 patients. Follow-ups for the primary endpoint are the 6-month visit and 12-month visit, depending on the Raymond Roy score at the 6-month visit. Total duration of enrollment (6 months), follow-up duration for primary endpoint (6-12 months), 24 months follow-up and reporting (3 months) will take approximately 33 months.

Any patient who is consented but has no implant attempt will be study exited.

All patients must be consented prior to performing study related procedures. All patients that provide consent and are implanted will be followed according to the follow-up schedule. Any patient for whom a failed implant attempt is performed will be followed for 1-month or until resolution of any potential device or implanted related adverse events, whichever occurs last.

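### Safety rests on DSMB judgement, but no event count or rate makes the combined committee meet, and at planned accrual no second scheduled review need fall before patient 51

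*Combined protocol and SAP*

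**What the plan says.** **Who judges safety.** Section 10 says the study is not powered for statistical significance and leaves the assessment of safety and performance to clinical judgement, supplied by the DSMB during the study.

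**When the committee meets.** Section 9.2 requires a review after five patients. It then says "The DSMB will provide further evaluation at least twice per year and after the first 5 patients are enrolled", and adds "If slow enrollment occurs, the DSMB may meet less frequently". It also says "The CEC and DSMB will meet as a combined committee", so the schedule covers both bodies. On the first review it says "Enrollment of further patients will occur as the DSMB reviews the data". Section 9.1 says "The CEC will regularly review and adjudicate the adverse events and any deaths" but names no interval.

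**Planned pace.** Section 11.5: "It is expected that the study will take 6 months to enroll a minimum of 51 patients".

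**What can stop the study.**
- Section 12.2.13 has the one stop worded as a sponsor obligation: "If an investigation shows that a USADE presents an unreasonable risk to subjects, the sponsor will terminate all investigations or parts of investigations".
- Section 12.2.15 lets the sponsor suspend for a high rate of known adverse events, as an option and with no rate given.
- Section 7.12 lists a DSMB recommendation as a possible reason for early termination.

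**Other safety looks.** Section 10.5 sends a summary covering safety to ethics committees and regulators after 10 patients. Section 12.2.13 makes the sponsor responsible for CEC review of serious neurologic, device-related and procedure-related events.

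**The anticipated rates.** Table 5 puts ischemic CVA, hemorrhagic CVA, aneurysm rupture and vessel perforation/rupture each below 5%. Section 6.1.1 says residual risks are addressed in "sections of the Instructions For Use as well as listed in Table 5".

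**The concern.** The committee whose judgement carries the safety assessment is called by the calendar, not by events. The calendar is coarse against the planned enrollment period. The plan states what it expects for each serious neurological event, yet nothing happens automatically when the observed count contradicts that expectation.

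The obligatory stop in 12.2.13 does not close this gap. It needs an unanticipated serious adverse device effect that the sponsor finds an unreasonable risk. Stroke and rupture are listed as anticipated. Table 9 does allow an event to be unanticipated by incidence, but it measures this against the risk analysis report, and the plan gives no incidence figure for that test.

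Section 18.1 states that all human use of this implant so far is compassionate use. Proctoring and sponsor attendance (5.3), patient-selection votes (9.3) and 62 patients with the first-generation device (18.2) lower the risk. None of them calls a meeting.

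**Working it through.** The plan states no safety-stopping figure, so there is none to reproduce. The inputs from the plan are 51 patients in 6 months (11.5), the review schedule (9.2) and the below-5% entries (Table 5). The true event rates of 10%, 15% and 20% are assumptions.

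**1. Timing of reviews**
- Accrual: 51 / 6 = 8.5 patients per month.
- Patient 5 enrolls at 5 / 8.5 = 0.59 months, and patient 51 at 6.0 months.
- A review six months after patient 5 falls at 0.59 + 6 = 6.59 months, after patient 51.
- If enrollment takes T months at an even pace, that review precedes patient 51 only when 5T/51 + 6 < T, so T > 6 × 51 / 46 = 6.65 months.
- Beyond 6.65 months the slow-enrollment clause allows fewer meetings. A minimum of two a year also does not require even spacing.
- The 10-patient summary is reached at 10 / 8.5 = 1.18 months.

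**2. What the early looks can show, for one event type**

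| Assumed true rate | ≥1 event in 5 | ≥2 events in 5 | ≥2 events in 10 |
|---|---|---|---|
| 10% | 41% | 8% | 26% |
| 15% | 56% | 16% | 46% |
| 20% | 67% | 26% | 62% |

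The formulas are 1 − (1 − p)^n and the binomial tail P(X ≥ 2 | n, p). A judgement-based review could act on a single event, so the 5-patient look is not worthless. If no one acted on anything afterwards, patients 6 to 51 would be expected to contribute 46 × 0.10 = 4.6, 46 × 0.15 = 6.9 or 46 × 0.20 = 9.2 events of that type.

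**3. Limits based on Table 5**

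For each number treated n from 2 to 51, take the smallest k ≥ 2 with P(X ≥ k | n, 0.05) ≤ 0.05.

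| Events of one type | With at most n treated | P at that n if the true rate is 5% |
|---|---|---|
| 2 | 7 | 0.044 |
| 3 | 16 | 0.043 |
| 4 | 28 | 0.049 |
| 5 | 40 | 0.048 |
| 6 | 51 | 0.041 |

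**4. Chance that the limits are reached**

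Exact recursion over 51 subjects, one event type, counted after every subject:

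| True rate | P(trigger) |
|---|---|
| 2% | 1.2% |
| 3% | 3.1% |
| 5% (ceiling) | 11.6% |
| 10% | 53% |
| 15% | 86% |
| 20% | 97% |

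This treats each outcome as known before the next implant. With a lag of 9 implants (30 days at 8.5 per month, the worst case for a 30-day event), the last three rows become 47%, 79% and 94%.

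**5. Four event types, if independent**
- 2% each: 1 − (1 − 0.0117)^4 = 4.6%.
- 3% each: 1 − (1 − 0.0315)^4 = 12%.
- 5% each: 1 − (1 − 0.1156)^4 = 39%.
- A total of 15% spread evenly (3.75% each): about 20%.

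**The case against.** Section 10 openly chooses judgement over statistical rules, and the plan is not short of safety oversight. SAEs reach the sponsor within 48 hours. The sponsor must ensure CEC review of serious neurologic events and must report SAEs to ethics committees and site investigators in a timely way. The 10-patient summary is a required external look during enrollment. The DSMB can recommend termination and the sponsor can suspend at any time.

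That stands, and it rules out two stronger readings. A reader might infer that the five-patient review is the only required safety look during enrollment. Section 10.5 contradicts this. A reader might also infer that the committee need not see SAEs until enrollment ends. Sections 9.1 and 12.2.13 call for regular CEC review and for review of all serious neurologic events, and the CEC and DSMB are one committee. Reading regular as possibly never is a worst case, not the evident intent. What survives is narrower: none of these provisions fixes a date, count or rate that obliges the committee to meet.

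The timing gap is also narrow. It rests on the expected pace, and 6.59 months is only just past 6.0. Section 9.2 can be read as making further enrollment depend on the five-patient review, or as letting enrollment continue during it, in which case that review may itself come after patient 6. Neither reading sets a later meeting.

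Table 5 is an imperfect yardstick. It gives broad bands for endovascular treatment in general, with no time window and no restriction to serious events. The 30-day SAE criterion and the choice of four rows are proposals of this review. Other hemorrhagic and occlusive events also listed below 5% are left out, and the four chosen types overlap clinically, so the independence figures are only a guide. Incidence limits may exist in the risk analysis report, which was not available.

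**Conclusion.** The point holds in limited form. The plan rests safety on DSMB judgement, yet no event count or rate convenes the combined committee. At the planned pace no second scheduled review need fall before patient 51. If enrollment runs past about 6.65 months, an evenly spaced review would fall in time, unless the slow-enrollment clause is used.

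An event trigger is a cheap improvement to patient safety, not the repair of a plan without oversight. The expected counts of 4.6, 6.9 and 9.2 describe patients 6 to 51 only if no one acts, and the existing reporting duties make that unlikely. The firm part is the obligatory meeting. An automatic hold on implanting and the exact limits are open to debate, because type-by-type counting would trigger in up to 39% of studies if all four types sat at the 5% ceiling and would miss most evenly spread excesses. The operating figures rest on the assumed true rates, on independence across types, and on Table 5 as the reference.

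**What to change.** Add to 9.2, with cross-references from 12.2.13 and 12.2.15:

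> The combined CEC/DSMB meets within 7 days, and advises in writing whether implanting should pause, when the number of treated subjects (implanted or attempted) with the same Table 5 event (ischemic CVA, hemorrhagic CVA, aneurysm rupture, or blood vessel perforation/rupture), reported as an SAE within 30 days of the procedure and regardless of relatedness, reaches 2 with at most 7 subjects treated, 3 with at most 16, 4 with at most 28, 5 with at most 40 or 6 with at most 51. The 10-patient interim summary (10.5) is also sent to the committee.

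The USADE rule and the discretion of the DSMB and sponsor stay as they are. A hold on new implants until the committee meets is an option for the sponsor. Seven days delays about 8.5 × 7 / 30 = 2 implants, plus any wait for the written advice.

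**Cost:** a running count from SAE reports already due within 48 hours (8.3), an occasional unneeded meeting, and a CIP amendment notified to or approved by ethics committees and regulators (12.2.4). No new committee, patients or procedures are needed.
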